3 STUDY DESIGN AND EVALUATION

3.1 Study Design

This will be a single-center, open-label, non-randomized, proof-of-concept study in recipients of living or deceased donor renal transplants (DDRTs). Twenty renal transplant patients will be enrolled, at least 10 of which will be recipients of DDRTs. At the time of transplantation, participants will be given alemtuzumab, 30mg intravenously over three hours. Participants will receive combination maintenance therapy with sirolimus and belatacept for at least one year. Patients' absolute lymphocyte counts (ALCs) and percent expression T cell of Ki67 will be assessed monthly. After one year of therapy, participants may consent to and begin sirolimus withdrawal or continue therapy through study close. Patients wishing to withdraw from sirolimus will begin sirolimus weaning when their ALC has reached at least 80% of baseline and had two consecutive monthly assessments of their percent expression of Ki67 fall within at least one standard deviation of the Ki67 expression of a healthy control population. Weaning will be triggered of the Ki67 expression, with other surface phenotype assessments being followed observationally. Patients meeting these parameters will be weaned off of sirolimus by halving the dose and/or increasing the dosing interval over at least a three-month period. Each dose reduction will require stable (within 1 standard deviation) peripheral Ki67 expression. After sirolimus is discontinued, patients will remain on belatacept monotherapy indefinitely. Clinical and mechanistic observation will continue for the duration of the study to assess the efficacy and safety of this approach. Subjects will be followed for at least five years.

Duration of Study

Subjects will be followed for at least five years. Belatacept is now approved by the FDA. Therefore, subjects remaining on belatacept at the conclusion of their five-year participation would be eligible to continue this therapy. If at the conclusion of this study belatacept is not commercially available to patients, the Principal Investigator will discuss other treatment options utilizing approved immunosuppressive therapies with the subject. If subjects are successfully weaned from sirolimus as a result of their participation in this protocol, there will be no need for consideration of alternative therapy.

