6.4 Discontinuation of Therapy

Belatacept therapy **MUST** be immediately discontinued for the following reasons:

- Withdrawal of informed consent (subject's decision to withdraw for any reason)
- Any clinical adverse event, laboratory abnormality or intercurrent illness which, in the opinion of the Investigator, indicates that continued treatment with study therapy is not in the best interest of the subject
- Pregnancy
- Missing 2 consecutive belatacept infusions, unless the subject is receiving lymphocyte-depleting therapy or has approval by the medical monitor to remain in the study
- Subjects receiving 56 consecutive days of dialysis and the investigator has determined that the subject no longer requires immunosuppression as the graft is functionally lost

- Imprisonment or the compulsory detention for treatment of either a psychiatric or physical (e.g., infectious disease) illness.

Subjects who are discontinued from study therapy must be followed for safety for 8 weeks post-study drug discontinuation.

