6.8 Withdrawal of Subjects from Study

Subjects will be removed from the study for the following reasons:

1. Withdrawal of informed consent (subject's decision to withdraw for any reason)
2. Any clinical adverse event, laboratory abnormality or intercurrent illness which, in the opinion of the Investigator, indicates that continued treatment with study therapy is not in the best interest of the subject
3. Pregnancy
4. Missing 2 consecutive belatacept infusions, unless the subject is receiving lymphocyte-depleting therapy or has approval by the medical monitor to remain in the study
5. Subjects requiring dialysis for 56 consecutive days and the investigator has determined that the subject no longer requires immunosuppression as the graft is functionally lost
6. Imprisonment or the compulsory detention for treatment of either a psychiatric or physical (e.g., infectious disease) illness.

Subjects who are discontinued from study therapy will be followed for safety for 8 weeks post-discontinuation.

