11.6 Reporting of AE Information Following Study Completion

Collection of safety information following the end of investigational product administration is important in assisting in the identification of possible delayed toxicities or withdrawal effects. All SAEs must be collected which occur within 56 days of discontinuation of dosing or completion of the subject's participation in the study if the last scheduled visit occurs at a later time. In addition, the Investigator should report any SAE which may occur after this time period which they believe to be certainly, probably or possibly related to investigational product. Finally, all events of death, graft loss, malignancy, PTLD, and serious infections (i.e., otherwise meeting SAE reporting requirements) must be reported for all randomized subjects until the end of the study, irrespective of study drug discontinuation or investigator-deemed causality.

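### Once a subject is stopped from belatacept and removed, later rejection and donor-specific antibody have no required route into the 3- and 5-year outcomes

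*Combined protocol and SAP*

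**What the plan says.** **Follow-up and removal.** Section 3.1 states: "Subjects will be followed for at least five years". Section 6.4 gives six reasons for an immediate belatacept stop: withdrawn consent, an adverse event or illness that makes treatment unwise, pregnancy, missed infusions, a functionally lost graft on dialysis, and detention. The missed-infusion item reads "Missing 2 consecutive belatacept infusions, unless the subject is receiving lymphocyte-depleting therapy or has approval by the medical monitor to remain in the study". The section ends: "Subjects who are discontinued from study therapy must be followed for safety for 8 weeks post-study drug discontinuation". Section 6.8 begins "Subjects will be removed from the study for the following reasons", lists the same six reasons, and ends "Subjects who are discontinued from study therapy will be followed for safety for 8 weeks post-discontinuation".

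**Reporting after a stop.** Section 11.6 says "All SAEs must be collected which occur within 56 days of discontinuation of dosing", or up to the end of participation where the last scheduled visit falls later. Beyond that, the request narrows to "any SAE which may occur after this time period which they believe to be certainly, probably or possibly related to investigational product". A fixed list (malignancy, PTLD, serious infection, graft loss, death) runs to study end whatever the cause or drug status, but for randomized subjects. Rejection and DSA are not on it.

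**What the analysis needs.** Section 3.3 includes biopsy-proven acute rejection by years 1, 3 and 5, and alloantibody formation. Section 4.1 uses all transplanted patients for efficacy (its wording also says randomized). Section 4.2 reports incidence outcomes as proportions with exact confidence intervals.

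**Replacement therapy.** Section 6.3.1 names a conventional regimen after early dialysis. Section 6.2 provides individual maintenance when sirolimus weaning is not successful, and a CNI-based regimen after steroid-resistant or antibody-mediated rejection. Section 6.6 covers steroid-resistant rejection. Section 3.1 closes a paragraph on drug supply at study end with this, on patients whose weaning succeeds: "weaned from sirolimus as a result of their participation in this protocol, there will be no need for consideration of alternative therapy".

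**The concern.** Patients on belatacept monotherapy are the ones who reached the regimen under test, and belatacept is their only maintenance drug. If it is stopped for a reason other than rejection while the graft works, the plan removes them and requires 8 weeks of observation. The protocol itself expects trouble in patients left without cover. Section 1.2 says that those who stopped maintenance after depletion all had acute rejection, although it was reversible. Section 1.3.5 judges complete weaning too risky. Section 11.6 names withdrawal effects as one purpose of collecting data after dosing.

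If late rejections in these patients are not recorded while they stay in the denominator, the 3- and 5-year rejection proportions come out too low. The loss is selective, because it follows from stopping the study drug.

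**Working it through.** The plan gives no figure on this point, so the check sets the sections side by side and then sizes the gap.

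**1. What must be captured after the window in a removed subject (section 11.6)**

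| Late event | Route | Required? |
|---|---|---|
| Graft loss, death, malignancy, PTLD, serious infection | Fixed list | Yes, if the list covers the subject |
| Rejection that is an SAE judged at least possibly related | Late-SAE sentence | Should be reported |
| Rejection that is an SAE judged unrelated | None | No |
| Non-serious or subclinical rejection | None | No |
| New DSA without such an SAE | None | No |

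Three other places bear on the last three rows.
- The causality scale in section 11.3 allows an event to be called not related when it has no temporal link to dosing, including when the drug is not being taken. A late rejection off drug can fit that.
- Section 9.2 cites subclinical rejection in up to 30% of stable grafts.
- Section 8.1 schedules anti-donor antibody yearly in long-term follow-up, so an 8-week window may contain no test.

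**2. Whom the fixed list covers.** Section 1.3.5 describes the first cohort as randomized (to donor marrow or not). Section 3.1 calls the current study non-randomized. Read literally, the list does not reach the second cohort.

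**3. Drug remaining when the window closes.** Half-life 176–210 hours (section 1.3.2, single doses, healthy volunteers). Fraction left = 0.5^(hours ÷ half-life).
- Day 28: 672/176 = 3.82 and 672/210 = 3.20 half-lives, so 7.1% and 10.9% remain.
- Day 56: 1344/176 = 7.64 and 1344/210 = 6.40 half-lives, so 0.50% and 1.18% remain.
- If the 8 weeks instead start at the second missed infusion (day 56), the window ends at day 112, or 12.8–15.3 half-lives, and includes some drug-free time.

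**4. Calendar.** Year 3 is week 3 × 365.25/7 = 156.5; year 5 is week 260.9. Under section 6.2 monotherapy can begin at about week 53 + 4 + 4 = 61. With an 8-week window, a stop before week 156.5 − 8 = 148.5 leaves both assessments outside it. A stop before week 260.9 − 8 = 252.9 leaves year 5 outside. For example, a stop at month 24 (week 104.4) leaves 260.9 − 104.4 = 156.5 weeks of planned follow-up, of which 8, or 8/156.5 = 5.1%, are required.

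**5. Effect of one missed rejection.** 1/20 = 5 points; 1/40 = 2.5 points if both cohorts are pooled. Illustration with exact 95% intervals: 4/20 = 20% (5.7–43.7%) against 5/20 = 25% (8.7–49.1%).

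**6. How many stops.** The documents do not say. In the first cohort all 20 patients tolerated belatacept (section 1.3.5): 0/20, exact upper limit 16.8%. Appendix C gives (13 + 15)/(74 + 71) = 28/145 = 19.3% stopping for adverse events in year 1 under a different regimen, which is an upper-end figure only. For about 12 weaned patients (section 3.4), 12 × 0.168 = 2.0 and 12 × 0.193 = 2.3, so roughly 0 to 2 stops. These are stops, not missed rejections.

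**The case against.** Section 11.6 governs adverse-event reporting, not efficacy data, and other routes exist. Section 3.1 promises five years. The section 4.1 database keeps graft function, medication and a running account of each patient's course, reported to UNOS standards. The yearly antibody test in section 8.1 carries no on-drug condition. This has weight, and a conscientious site may well record a late rejection. But section 6.8 is the specific rule for these subjects. It removes them, and nothing says that the general provisions survive removal.

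A reader might go further in three ways that the documents do not support.
- **That section 3.1 tells sites to give nothing after a mid-study stop.** The sentence closes a paragraph about the end of participation, directly after a promise to discuss alternatives if belatacept is unavailable. It may mean only that sirolimus needs no substitute. Its fault is a missing condition.
- **That the plan provides no replacement therapy.** The individual-maintenance clause in section 6.2 has no rejection condition. A patient stopped before 365 days on belatacept alone fails the section 4.2 definition and can reasonably be read as covered. The clear gap is a stop after 365 days, which a transplant physician would normally fill. Section 7.6 addresses PTLD and PML, and section 11.10 pregnancy. Section 7.5 and part of section 1.3.5 were not in the text available, so an instruction there cannot be excluded.
- **That late rejection never needs reporting.** SAEs judged related, and graft loss, remain reportable, and the 56-day window can extend to a later scheduled visit.

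It is also fair that the primary definition in section 4.2 and the sample size are untouched, and that the efficacy analysis is descriptive.

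**Conclusion.** The recording gap holds and should be closed. After the section 11.6 window, subclinical, non-serious or unrelated-judged rejection, and DSA, in a removed subject have no required capture. That conflicts with sections 3.1, 3.3 and 4.1. On a first-order decline with the healthy-volunteer half-life, the window counted from the last dose closes with about 0.5–1.2% of drug left, which is about when an unreplaced monotherapy patient becomes drug-free.

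The practical size is probably small. The frequency of stops is unknown. A missed event also needs a first rejection that starts after the window and escapes every other record. One such event moves a proportion by 5 points with 20 patients. No share of stops missing year 3 or year 5 is claimed, because that would require an assumed distribution of stop times. The wording of section 3.1 and the replacement clause in section 6.2 are secondary.

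**What to change.** 1. **Section 11.6.** Add biopsy-proven rejection and de novo DSA, from tests done in routine care, to the events reported to study end irrespective of discontinuation. Apply the list to all transplanted subjects instead of randomized ones.
2. **Section 6.8.** State that subjects stopped from study therapy remain in outcome follow-up for these events through five years unless they withdraw consent to follow-up. Without this, the change to 11.6 would still sit beside a rule that removes the subject after 8 weeks.
3. **Minor wording.** End the last sentence of section 3.1 with *provided belatacept continues*. Extend the individual-maintenance clause in section 6.2 to any monotherapy patient with a functioning graft whose belatacept is stopped, including after 365 days. Because the clause is individual, it leaves room for PML, PTLD, severe infection and pregnancy.

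The cost is a few sentences and slightly more follow-up reporting. No study tests are added, and the sample size and the section 4.2 endpoint definition do not change.

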3.2 Study Population

Adult, EBV seropositive patients who do not have evidence of DSA pretransplant and who are scheduled to receive a kidney transplant at Emory University. Candidacy for

transplantation will be determined using the standard methods of evaluation active at Emory during the study period.

3.3 Criteria for Evaluation

1. Number of patients successfully withdrawn from sirolimus for 12 months after last dose of sirolimus
2. Biopsy proven acute rejection or chronic allograft nephropathy by 1, 3 and 5 years
3. Evidence of donor-specific hyporesponsiveness by MLR and ICCS
4. Evidence of regulatory T cell and transitional B cell activity in the periphery and allograft
5. Donor specific and third party alloantibody formation

3.4 Sample Size Determination

Our prior experience with alemtuzumab, belatacept and sirolimus, in recipients of live donor kidneys suggests that this regimen is very effective in preventing acute rejection, with only one steroid sensitive, clinical rejection episode seen in the first year. However, with the liberalization of the inclusion criteria, it is anticipated that an acute rejection rate prior to initiation of sirolimus withdrawal of up to 20% will exist, excluding up to four patients from eligibility for sirolimus withdrawal. It also is anticipated that four additional patients will either not meet other criteria for withdrawal or will refuse to be withdrawn from immunosuppression. The number of patients has therefore been chosen to have approximately 12 patients who are eligible for sirolimus withdrawal and in whom withdrawal is attempted, in order to establish a reasonable proof-of-concept. This target of 12 subjects in whom sirolimus withdrawal is attempted will allow for the detection approximately 6 subjects successfully withdrawn from sirolimus for one year, assuming the probability of a subject in whom withdrawal is attempted being successfully withdrawn from sirolimus for one year is 50%, a rate determined by the current cohort. Since there are no trials exploring monotherapy belatacept reported in the literature or registered with ClinicalTrials.gov, this cohort of patients withdrawn successfully will represent a significant finding.

3.5 Interim Analyses

No interim analysis is planned.

4 STATISTICAL METHODOLOGY

4.1 Data Set Descriptions

A summary of all patient data will be kept in a study database developed for this study. In addition to the experimental data, this database will include recipient and donor demographics and transplant relevant medical history (comorbidities, HLA type, etc.), graft function, immunosuppressive medications and levels, and a running summary of the patient's post transplant course. Data will be recorded and reported in accordance with the standards required by the United Network for Organ Sharing (UNOS). The data set will consist of all patients who are randomized and transplanted and will be used for all

efficacy analyses. The as-treated data set will consist of all patients who receive at least one dose of belatacept and will be used for all safety analyses. Subgroup analyses will be performed for selected endpoints in subjects whom withdrawal was attempted and not attempted in order to provide supporting information to the main analyses. Demographic and baseline characteristics of patients will be summarized descriptively by treatment group, by means and standard deviations (SDs) for continuous variables and frequency distribution for categorical variables. Summaries will be performed based on the data set.

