6.1 Transplant-specific therapies

Alemtuzumab

At the time of transplantation (in pre-op holding or the operating room) patients will be given a single dose of methylprednisolone 500 mg intravenously over 30 minutes followed by acetaminophen 650 mg orally or rectally and diphenhydramine 50 mg intravenously, followed in 1 hour by alemtuzumab, 30mg, given intravenously over 3 hours.

Transplantation

Transplantation will be performed using standard surgical techniques for organ

engraftment. An 18-gauge needle core biopsy will be obtained from the allografted kidney 30 minutes to 1 hour after reperfusion. These will be divided for routine histology, immunohistochemistry (2/3 of biopsy) and RT-PCR analysis (1/3 of biopsy) snap frozen on site. Patients will be cared for perioperatively on the transplant unit. Technical aspects of the postoperative management (Foley catheterization, ureteral stenting, etc) will be according to the standard of care as determined by the attending surgeon.

Belatacept

Belatacept will be given within 24 hours of transplantation via a peripheral intravenous catheter at a dose of 10mg/kg infused over 30 minutes. The dose will be repeated on study days 4 (post op day 3) and 8 (post op day 7), then every 2 weeks for 5 additional doses. Thereafter, belatacept will be given once every 4 weeks (+/- 3 days) at 10mg/kg through 6 months then at 5mg/kg indefinitely.

Sirolimus

Sirolimus will be started on postoperative day 1 at a dose of 2 mg per day orally. Doses will be adjusted to maintain 24 hour trough levels of 8-10ng/ml until the drug is weaned as described below. Sirolimus has been associated with delayed graft function in organs affected by acute tubular necrosis. Therefore, in the unlikely event that patients experience delayed graft function (<5% of live donor transplants experience delayed graft function), defined as inadequate renal function to avoid dialysis by post-operative day 7, maintenance therapy will be changed to mycophenolate mofetil (1.5 gm twice daily) and prednisone (30mg daily) until graft function improves. Patients will then be converted to sirolimus.

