6.3 Treatment Administration

Infusion of Alemtuzumab shall begin within 24 hours of surgery, and shall be given prior to belatacept.

Infusion of the first belatacept dose should begin no later than 24 hours of surgery but not prior to the surgeon having made an initial intraoperative assessment and has concluded that the subject remains a transplant candidate and the transplant will proceed. Infusion doses will be based on the subject's body weight at enrollment, and will not be modified during the course of the study, unless there is a change of body weight $\pm 10\%$. Belatacept should be administered to the subject at a relatively constant rate over 30 minutes.

Sirolimus will begin orally within 48 hours of surgery and after both belatacept and alemtuzumab.

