7.6 Immunosuppressive Therapy-specific risks

Alemtuzumab

Alemtuzumab is known to have a significant risk of cytokine release syndrome. This syndrome can usually be minimized by premedication with steroids but can include fever, chills, malaise, hypotension, tachycardia, and pulmonary edema. Lymphopenia may be associated with increased risk of infection.

Sirolimus

Phase III studies of sirolimus in cyclosporine based regimens have revealed mild dose related thrombocytopenia and increases of serum triglycerides and cholesterol. This latter finding is probably its most consistent effect and was seen in 40-50% of patients. Hypertriglyceridemia predominates. HMG-CoA reductase inhibitors and fibric acid have been used and well tolerated to counteract the hyperlipidemia associated with sirolimus. Additionally, the unexpected finding of nephrotoxicity has been encountered but is likely attributable to sirolimus' potentiation of CNI nephrotoxicity and thus is likely to be inapplicable in this trial. Other common events reported in trials include leukopenia, hypertension, anemia, nausea, vomiting, elevated liver enzymes, rash and acne [37,38] Other risks from the package insert for sirolimus include possible development of lymphoma and other malignancies, particularly of the skin, increased susceptibility to infection including opportunistic infections, fatal infections, and sepsis, and lymphocele, a known surgical complication of renal transplantation, occurring significantly more often in a dose-related fashion in sirolimus-treated patients.

Belatacept in Kidney Transplant Study

Specific risks associated with belatacept may include those typically associated with transplant related immunosuppression including infection and malignancy.

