11.3 Collection of Safety Information

An *Adverse Event (AE)* is defined as any untoward medical occurrence in a patient or clinical investigation subject administered a pharmaceutical product and that does not necessarily have to have a causal relationship with this treatment. An AE can therefore be any unfavorable and unintended sign (including an abnormal laboratory finding, for example), symptom, or disease temporally associated with the use of a investigational (medicinal) product (IP), whether or not considered related to the IP.

During clinical trials, adverse events can be spontaneously reported or elicited during open-ended questioning, examination, or evaluation of a subject. (In order to prevent reporting bias, subjects should not be questioned regarding the specific occurrence of one or more adverse events.)

Following the subject's written consent to participate in the study, all serious AEs should be collected, including those thought to be associated with clinical trial procedures. The collection of non-serious AE information should begin at initiation of investigational product. Non-serious AE information should also be collected from the start of a placebo lead-in period or other observational period intended to establish a baseline status for the subjects. Following study completion, any SAE thought to be related to study drug or clinical trial procedures should also be reported.

Certain adverse events occur commonly in this study population and will not be recorded as an adverse event, unless it is believed to be associated with the study medications (Alemtuzumab, Sirolimus, Belatacept) and/or it meets the definition of a serious adverse

event. This list is inclusive of, but not limited to events noted below, and will be at the discretion of the Principal Investigator.

Occurrence of:

- Post-op pain.
- Isolated upper respiratory infection, nasopharyngitis, cough, dyspnea and bronchitis.
- Isolated episodes of diarrhea, constipation, nausea, abdominal distention and vomiting.
- Hypokalemia/hyperkalemia, hyponatremia/hypernatremia, hypocalcemia, hypercalcemia, hypophosphatemia/hyperphosphatemia, /hypomagnesemia,/hypermagnesemia, hyperuricemia and hyperglycemia
- Peripheral edema
- Hematuria, proteinuria, glycosuria and dysuria.
- Headache, dizziness, tremor, insomnia, anxiety, fatigue and depression.
- AVF thrombosis and renal artery stenosis.

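### The safety set requires a belatacept dose although alemtuzumab is always given first, so a patient exposed only to alemtuzumab is left out of the planned safety tables

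*Combined protocol and SAP*

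**What the plan says.** Section 4.1 names two analysis sets. The set for every efficacy analysis is introduced with the words "The data set will consist of all patients who are randomized and transplanted and will be used for all". (The study is non-randomized according to Section 3.1, so I read this as the transplanted patients.) For safety, the as-treated set is defined as "all patients who receive at least one dose of belatacept and will be used for all safety analyses". The safety analyses in Section 4.2 name no other population.

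On the order of the drugs, Section 6.3 states: "Infusion of Alemtuzumab shall begin within 24 hours of surgery, and shall be given prior to belatacept". The start of the first belatacept infusion has an outer limit of 24 hours from surgery. It must also wait for the decision that the operation goes ahead; the wording of that condition is "not prior to the surgeon having made an initial intraoperative assessment and has concluded that the subject remains a transplant candidate". Section 6.1 opens the alemtuzumab sequence with premedication: "At the time of transplantation (in pre-op holding or the operating room) patients will be given a single dose of methylprednisolone 500 mg". The alemtuzumab infusion follows an hour later and runs for 3 hours.

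Section 11.3 lists alemtuzumab, sirolimus and belatacept together as the study medications. Section 7.6 says: "Alemtuzumab is known to have a significant risk of cytokine release syndrome". On collection, Section 11.3 gathers serious events from consent, and for the rest says: "The collection of non-serious AE information should begin at initiation of investigational product".

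**The concern.** The primary objective concerns a sequence: depletion with alemtuzumab, followed by belatacept and sirolimus. A safety set for that regimen should begin with the first drug of the sequence. This one begins with the second. Entry therefore depends on something that happens after exposure has started: the patient must have come through the alemtuzumab step and reached belatacept.

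That selection works in one direction. A reaction to alemtuzumab severe enough to keep the patient from belatacept is an event of most interest for the first component, and it is what the definition removes. If the transplant does not proceed, the patient is in neither analysis set. In a cohort of 20, one omitted patient can decide whether a rare serious event appears in the tables at all.

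**Working it through.** **Text check.**

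| Step | Source | Content |
|---|---|---|
| Safety set | 4.1 | at least one belatacept dose |
| Efficacy set | 4.1 | transplanted |
| Order | 6.3 | alemtuzumab before belatacept in every patient |
| Condition on belatacept | 6.3 | surgeon's intraoperative confirmation; up to 24 hours from surgery |
| Status of alemtuzumab | 11.3, 7.6 | study medication with its own acute risk |
| Other safety population | 4.2 | none |

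So alemtuzumab without belatacept is possible under the plan, and such a patient is not in the safety set. Membership of the efficacy set then depends on whether the transplant took place:

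- Transplanted, no belatacept: in the efficacy set, not in the safety set.
- Transplant abandoned after alemtuzumab: in neither.

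**Size.** The plan states no figure to reproduce.

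*Inputs.* N = 20 new patients (Section 3.1). The per-patient probability p of alemtuzumab without belatacept is not in the documents; I assume 1%, 2% and 5%.

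*Chance of at least one such patient:* 1 − (1 − p)^20.

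| Assumed p | 1 − (1 − p)^20 | Expected number, 20p |
|---|---|---|
| 1% | 1 − 0.99^20 = 18% | 0.2 |
| 2% | 1 − 0.98^20 = 33% | 0.4 |
| 5% | 1 − 0.95^20 = 64% | 1.0 |

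*Effect of one omitted patient.* Suppose this patient has an event and k of the other 19 also have it. The rate changes from k/19 to (k + 1)/20, a difference of (19 − k)/380.

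- k = 0: 19/380 = 5.0 percentage points. The report changes from 0/19 = 0% (exact 95% CI 0 to 17.6%) to 1/20 = 5.0% (0.1 to 24.9%).
- k = 4: 15/380 = 3.9 points.
- For an event this patient did not have, the rate falls from k/19 to k/20.

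If both cohorts are pooled to about 40 (Synopsis), the k = 0 case changes from 0/39 (0 to 9.0%) to 1/40 = 2.5% (0.1 to 13.2%).

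*In-document experience.* Section 1.3.5 reports that all 20 first-cohort patients received and tolerated the induction dose and that all tolerated belatacept. Zero in 20 has an exact two-sided 95% upper limit of 1 − 0.025^(1/20) = 17%, so it does not rule out any of the assumed rates. That cohort was live-donor only, whereas the new one requires at least 10 deceased-donor recipients (Section 3.1).

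**The case against.** The strongest reply is that little would be lost in practice. The interval between the two drugs is short, the first cohort had no trouble with induction, the analysis is descriptive, and oversight does not depend on the as-treated set. This stands, and it limits the size of the point. It does not answer the definition itself, which selects on tolerating the first drug.

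A reader might also infer more than the documents support:

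- *That serious events before belatacept go unreported.* They do not. Section 11.3 collects them from consent, and Section 11.2 sends them to the Board and has all adverse events reviewed weekly. The gap is in the planned tables and denominators.
- *That death or graft loss before belatacept disappears.* A transplanted patient stays in the efficacy set, and graft function and survival are secondary objective 7. Only an abandoned transplant falls outside both sets.
- *That one such event would stop the trial yet be missing from its tables.* Section 6.9 requires three of the first ten patients or five at any time; the enrolment halt needs two of five consecutive subjects within three months. One event triggers neither.
- *That one omitted patient shifts every rate by 5 points.* This holds only for an event nobody else has.
- *That non-serious events are uncollected between the two drugs.* Section 11.3 ties their collection to the investigational product. Appendix C calls belatacept the investigational agent, and Section 10.2 puts alemtuzumab under other agents. But Section 10 is headed in the plural and covers both, and the Month 1 schedule in Section 8.1 marks adverse events from enrollment. This is an ambiguity and does not demonstrate a gap.
- *That Sections 6.1 and 6.3 conflict on alemtuzumab timing.* They do not. The pre-operative location in 6.1 introduces the premedication, and the surgeon's confirmation in 6.3 applies to belatacept alone.

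**Conclusion.** The point holds as a defect in the definition of the safety set. Section 4.1 conditions all planned safety analyses on receiving the second drug of the regimen, so a patient exposed only to alemtuzumab is omitted, and the omission favours the regimen's first component.

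The expected effect is small: between 0.2 and 1.0 such patients in 20 under the assumed rates of 1% to 5%, and none if every patient goes on to belatacept. The size rests entirely on those assumed rates, because the documents give none. The defect itself rests only on the text of 4.1, 4.2 and 6.3. It deserves correction because the change is nearly free and because the omitted case could be the only occurrence of a serious event in a small cohort.

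**What to change.** In Section 4.1, define the safety set as all patients who receive any amount of alemtuzumab, belatacept or sirolimus under the protocol, and use it for all safety analyses.

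For consistency, state in Section 11.3 that non-serious event collection starts with the first study medication given, which agrees with the Month 1 schedule in Section 8.1.

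The cost is two sentences. No dose, timing or clinical rule changes, and no patients or procedures are added. The safety denominator may rise slightly and some rates may look slightly less favourable. If every patient who receives alemtuzumab also receives belatacept, the safety set is the same under either definition.
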